# KING'S College LONDON

#### STUDY PROTOCOL

#### **REVISION HISTORY**

Protocol version	Protocol date	Minor or substantial amendment	Date approved by Ethics	Date approved by HRA	Comments and description
V1.0	04/08/2017	N/A Initial version	N/A	N/A	N/A
V2.0	06/09/2017	N/A – part of initial submission	N/A – requested changes	N/A – requested changes	Updated as per request of JRMO. Additional information re the online ordering kits added along with additional detail re confidentiality.
V3.0	16/11/2017	N/A – part of initial submission	27/11/2017	18/01/2018	Updated as per request of the REC to correct typographical errors and to provide more detail on the consent processes.
V4.0	08/06/2018	SA 1	14/06/2018	28/06/2018	Updated with the detail that only two patient identifiers are now required on the sample label (was previously three)
V5.0	28/01/2019	SA 2	03/04/2019	04/04/2019	Update and refining of study aims & objectives including change to stand-alone feasibility pilot, update with new clinical pathway for follow up of HPV positives, change in study Sponsor (and associated data handling changes), reduced passive follow up period to duration of study only, revised study end date to 31 March 2020, updated how residual samples will be stored and handled. Updated details of third-party vendors, specifically Preventx who will take over the laboratory role from The Doctors Laboratory and new responsibilities for PSL Print Management Ltd.
V6.0	09/10/2019	SA 3	17/12/2019	24/12/2019	
 
To update the label of the sample tube in the opportunistic kits to include two identifiers
 
To add additional advice to the protocol and accompanying study documents for pregnant women.
 

Protocol version	Protocol date	Minor or substantial amendment	approved	Date approved by HRA	Comments and description
					
 
To update the wording in HPV results letters
 
To add extra information and clarification around the data required for the trial and purpose of obtaining the different types of data
 
To add a note to the PIS, and the self-sample instruction leaflet for the participant to contact the study team if they haven't received their test result within two weeks
 

V7.0	27 th April 2020	Minor amendment 3	N/A	N/A not submitted for HRA approval as per COVID guidance at the time	
 
Extension to passive follow up end date
 
Further details/clarification (and accompanying participant correspondence) added to the post study follow up procedures under care of GP
 

V8.0	23 rd June 2021	Minor amendment 4	25th June 2021	TBC	Update to end of trial definition
V9.0	12 th Oct 2021	Minor amendment 5	N/A	TBC	Upon study completion study records will be kept for 5 years as per agreement with Sponsor.

#### **GLOSSARY OF TERMS AND ABBREVIATIONS**

CCG	Clinical Commissioning Group
CI	Chief Investigator
CIN	Cervical Intraepithelial Neoplasia
GP	General Practitioner
GSTT	Guy's and St Thomas' NHS Foundation Trust
HCA	Health Care Assistant
HCP	Health Care Practitioner
HPV	Human Papillomavirus
JRMO	Joint Research Management Office
KCL	King's College London
NHAIS	National Health Authority Information System
NHSCSP	National Health Service Cervical Screening Programme
NHS REC	National Health Service Research Ethics Committee
PI	Principal Investigator
QMUL	Queen Mary University of London
REC	Research Ethics Committee
SSK	Self-Sampling Kit

#### **STUDY SYNOPSIS**

Chart Title	A Landan LIDV Call Compline Dilat			
Short Title	A London HPV Self Sampling Pilot			
	A pragmatic, factorial cluster randomised controlled pilot study (a 2 x3 factorial design, with the 3-way (individual level) randomisation nested within the 2-way (GP-level) randomisation.			
Methodology	GP practices will be randomised 1:1 to either offering self- sampling kits (SSK) opportunistically to women overdue (>6 months) cervical screening when they present for any reason (intervention arm) or usual care (control arm).			
	The second (nested) randomisation will be individual level randomisation of women within each GP practice who have never been screened or who reach the 15- or 27-month anniversary of the date their last cytology test was due without being screened (by self-sample or cytology). 2:1:1 to either: Group A Usual care (control). Group B Receiving a letter inviting them to order a kit, or Group C: Receiving a kit in the post.			
Research Sites	~13 GP practices in London			
Aim	To assess feasibility and optimal approaches for offering self-sampling to cervical screening non-attenders in London to increase coverage.			
Objectives	A summary table of study objectives, endpoints and method of assessment is located in Appendix 1 .			
	For GP-level randomisation:  ~8420 women in total will be eligible (i.e. >6m overdue cervical screening) within 13 GP practices of which we estimate the following:  • ~500 will be offered SSKs opportunistically (330 will accept and ~210 will return a self-sample)			
Number of participants	For individual-level randomisation:  • ~5000 (i.e. never screened or 15- or 27-month anniversary of the date their last cytology test) will be individually randomised  • ~2500 will receive an SSK or letter inviting them to order an SSK via individual level randomisation of which 175-300 will return a self-sample			
Inclusion criteria	
 
GP-level randomisation
 
Women aged 25-64 years who are eligible for cervical screening and are least 6 months overdue (i.e. no cervical cytology recorded in the GP records in the past 3.5 years if aged 25-49 or 5.5 years if aged 50-64)
 
			

·	
	Individual-level randomisation
	Never-screened women & women who reach the     15 months* of last smear due date (and not screened by smear or self-sample)      Women unable to provide informed consent (e.g.
	because of learning difficulties)
Exclusion criteria	
 
Women who are documented in the GP records as being a Type 2 objector (i.e. who have objected to disclosure of identifiable data by NHS Digital for secondary purposes) will not be individually randomised.
 

Statistical Methodology and Analysis	We will calculate summary statistics for groups of interest (e.g. uptake of self-sampling by mode of approach). Screening uptake between the three arms of the individual level randomisation will be compared by a Chi-square test (2 degrees of freedom).
Proposed Start Date	Initial start date: April 2018 (halted on June 2018) Re-start date: March 2019
Proposed End Date	March 2020 (Recruitment period) April 2021 (Follow up)
Study Duration	Up to 12 months (active recruitment) 6 months follow up (from date last HPV positive result on an ALOHA self-sample is reported) Please note: In light of the Coronavirus pandemic cervical screening services are currently restricted and/or paused (the situation differs locally). This has a knock-on effect to the 6 month follow up period (as per the secondary objective) and therefore this period will need to be extended accordingly.

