#### 4. STUDY DESIGN

A randomised controlled pilot in GP primary care using a 2x3 factorial design, with the 3-way (individual-level) randomisation nested within the 2-way (GP-level) randomisation (see Figure 1 Study Schematic).

Approximately 13 GP practices in Hounslow CCG (Clinical Commissioning Group) will be included initially. Additional GP practices and CCGs may be added as the study progresses.

The first randomisation will be GP practices in the ratio 1:1 to either:

- Intervention arm Offering self-sampling kits opportunistically to women overdue cervical screening by at least 6 months when they present to GP primary care for any reason, and
- 2. Usual care (control) women will receive the usual smear reminder letter.

Practices will be randomised in a single block of 12 (with 6 in each arm) using computergenerated random numbers. We may stratify by list size if there are large differences between participating practices.

The second (nested) randomisation will be individual level randomisation of women within each GP practice who have never been screened or who reach the 15-month anniversary of the date their last cytology test was due without being screened (by self-sample or cytology). Women who are already past the 15-month anniversary of their last test due date at study start will be randomised if they reach the 27-month anniversary (i.e. women who are between 16 and 27 months past their last test due date). This will allow all women who are overdue screening by at least 15 months to be randomised while avoiding inviting women to self-sampling too close to their next invitation (women aged 25-49 are invited every 36 months). Randomisation at the 27 month anniversary of last test due date will only take place for the first 12 months of the study. This will avoid women being randomised more than once. Never screened women will be randomised in batches throughout the study (e.g. according to birth month or by counting 15m from their last test due date if they had attended when invited), rather than all at a single time point.

Individual-level randomisation of women will be in the ratio of 2:1:1 to either:

[figure not shown]
- Group A: Usual care (control).
- Group B: Receiving a letter inviting them to order an SSK
- Group C: Receiving an SSK in the post.

The planned pilot trial duration is up to 12 months for the active recruitment phase.

Figure 1 Study Schematic

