#### 8.1.2. Individual level randomisation

With 13 GP practices we anticipate that some 5000 will be identified as never screened or will reach the 15- or 27-month anniversary of their last test due date during the study. Of these, approximately 2500 women will be randomised to each of the two intervention arms. If we assume that 12% of those who are sent a kit (initially) return an adequate sample, the expected 95% confidence interval would be estimated with approximately ±1%. If about 7% of those offered a kit request one and return an adequate sample, then this could be estimated with approximately ±1%. Therefore, for 13 GP practices approximately 1250 invitation letters will be sent (here, the number of self-sampling kits will depend on the women's willingness to participate) and 1250 self-sampling kits posted.

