#### 8.2. Planned analysis

The aim of the pilot study is to assess feasibility and optimal approaches for offering self-sampling to cervical screening non-attenders in London, therefore there is no formal primary outcome measure. Instead, we will calculate measures of feasibility and acceptability such as the proportion of eligible women who are offered kits, accept and return a self-sample for each arm. We will also examine how this differs by GP practice, age and cervical screening status. The Chi Squared test will be used to determine the

differences in proportions between groups. For HPV positive women we will calculate the proportion who have a follow-up investigation within six months.

Descriptive statistics will be used to compare demographic and cervical screening status between responders and non-responders.

We plan to estimate:

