#### Individually randomised women

- 1) The proportion of eligible women in Group B who order a self-sampling kit
- 2) The proportion of eligible women in Group B and Group C who return a self-sample.

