#### All women who return a self-sample and all individually randomised women

We will examine the passive follow up data to determine if we can extract:

 Change in cervical screening coverage at each practice (to assess the impact of selfsampling on coverage):

- Cervical screening status at the end of the passive follow up period (aggregate anonymous data and/or individual anonymous data for women who return a selfsample from GP records)
- 3) Cytology and histology (if available) results for women who return a self-sample (if applicable)
  - The proportion with abnormal cytology
  - The proportion with CIN2+ on histology

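### The three individually randomised groups are compared by a 2-df omnibus chi-square test on an undefined screening uptake, with no committed letter-versus-kit or intervention-versus-usual-care contrast

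*Protocol*

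**What the plan says.** The Statistical Methodology and Analysis row of the protocol synopsis makes two statements. Summary statistics will be calculated for groups of interest, with "uptake of self-sampling by mode of approach" as the example. Then: "Screening uptake between the three arms of the individual level randomisation will be compared by a Chi-square test (2 degrees of freedom". Screening uptake is not defined there or among the endpoints. The primary endpoint (2.4) is uptake of self-sampling, and Appendix 1 adds a window of 6 months after invitation.

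Section 8.2 says the study is a feasibility pilot, "therefore there is no formal primary outcome measure". It names a test in general terms: "The Chi Squared test will be used to determine the" differences in proportions between groups, without saying which groups or which outcome. For the individually randomised women it lists the proportion of Group B who order a kit, and "The proportion of eligible women in Group B and Group C who return a self-sample". Group A is not in that list. Screening status at the end of passive follow-up, for all individually randomised women, comes under a conditional lead-in: "We will examine the passive follow up data to determine if we can extract".

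On design, section 4 states: "Individual-level randomisation of women will be in the ratio of 2:1:1 to either" usual care (A), a letter inviting the woman to order a kit (B) or a posted kit (C). Section 8.1.2 gives the expected number: "With 13 GP practices we anticipate that some 5000 will be identified as never screened" or due at the 15- or 27-month anniversary. It assumes that 12% return an adequate sample after a posted kit and 7% after a letter.

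**The concern.** The stated aim (2.2) is to find the best ways of offering self-sampling so as to raise coverage. The primary objective (2.3.1) separates opt-out from opt-in, and Appendix 1 sets them against each other. A reader will want two answers from the individual randomisation: does posting a kit bring in more samples than a letter, and how much does either add to usual care?

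The one test explicitly tied to these three groups answers neither. A 2-df test asks only whether the three proportions are all equal. It does not say which groups differ or by how much. It is also attached to an outcome that can be read in two ways, and its behaviour differs between them. Half the women are allocated to usual care, and what the trial reports from them depends on which reading is meant.

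**Working it through.** **Inputs.** From section 4, the ratio is 2:1:1. From 8.1.2, the total is about 5000, with 1250 letters and 1250 kits, so A/B/C = 2500/1250/1250; assumed returns are 7% (B) and 12% (C). The protocol gives no significance level for the chi-square test. I assume two-sided 5%, in line with its 95% intervals.

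**The plan's own figure.** There is no power or sample size for the chi-square test. The nearest figure is the half-width of approximately ±1% for each uptake proportion in 8.1.2, by 1.96·√(p(1−p)/n):
- n = 1250: ±1.80 points at 12%, ±1.41 at 7%.
- n = 2500: ±1.27 points at 12%, ±1.00 at 7%.

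So ±1% fits the wording in the same section that puts 2500 women in each intervention group, not the 2:1:1 split of 5000. That inconsistency is a separate matter. I use 1250 per group below.

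**Method for the omnibus test.** Noncentrality = Σ nᵢ(pᵢ − p̄)² / [p̄(1 − p̄)], where p̄ is the weighted mean. Power comes from the noncentral chi-square distribution with 2 df.

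**Reading 1: self-sample return.**
- A 0%, B = C = 7%: p̄ = 0.035. The numerator is 5000 × 0.035² = 6.125 and the denominator 0.035 × 0.965 = 0.0338. Noncentrality is 181 and power above 99.99%.
- A 0%, B 7%, C 12%: noncentrality 284, power above 99.99%.
- A 0%, B = C = 1%: noncentrality 25, power about 99.7%.
- Group A need not be at zero, because section 5.3 includes women offered kits opportunistically in intervention practices. Assume half the women are in such practices and apply the 60% consulting and 9% returning of 8.1.1: 0.5 × 0.60 × 0.09 = 2.7%. With A 2.7% and B = C = 9.7%, p̄ = 0.062, noncentrality is 6.125 / (0.062 × 0.938) = 105, and power is still above 99.99%.

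On this reading the test rejects whether or not letter and kit differ.

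**Reading 2: any screening (cytology or self-sample).** The protocol gives no cytology uptake for Group A. I assume 5% to 30%; gains are in percentage points over A.

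| Gain in B, gain in C | Power, A = 5% | Power, A = 30% |
|---|---|---|
| +7, +7 | above 99.9% | 99.8% |
| +3.5, +3.5 | 99.6% | 66% |
| +3.5, +6 | above 99.9% | 93.9% |
| +1, +2 | 61% | 19% |

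Rejection is not certain here. The first two rows show that the test can still reject often when B and C are identical, so a significant result is not evidence about letter versus kit.

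**The direct contrast, C minus B, on self-sample return.**
- Half-width at 12% v 7%: 1.96·√(0.07 × 0.93/1250 + 0.12 × 0.88/1250) = 1.96 × 0.01169 = 2.3 points.
- Power at 12% v 7%: 99.0%.
- Power for smaller differences: 76.7% at 10% v 7% and 45.3% at 9% v 7%.

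**The case against.** The strongest reply is that the sentence does not test self-sample return at all. The same synopsis row gives self-sampling uptake its own phrase and assigns it to summary statistics. Elsewhere (synopsis, section 4 and 5.3) being screened covers self-sample or cytology. The natural reading is therefore any screening, which Group A can have. This stands. A reader might infer that the test is bound to be significant because usual care provides no kit, but that holds only on Reading 1, and even there Group A can return some samples through opportunistic offers.

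A reader might also infer that this is the only test in the protocol, or that letter and kit are never compared. The document does not support that. The general chi-squared test in 8.2 could cover B versus C, 8.2 estimates uptake in B and in C, and Appendix 1 sets opt-out against opt-in. Nor is it right that the usual-care women enter no comparison, since the synopsis test includes them. What remains is that no B-versus-C contrast is committed to.

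Third, this is an estimation pilot sized on interval width, and a statistical analysis plan that is not shown may name the contrasts. A global test can also act as a gatekeeper: with exactly three groups, unadjusted pairwise tests after a significant global test control the familywise error. This lowers the weight of the point, and it makes multiplicity adjustment and stratification by practice optional. It does not rescue the sentence. The protocol has already fixed a method without fixing its outcome, and in an estimation study a difference with an interval serves better than an omnibus p-value.

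Last, 10.5 limits control women to anonymous aggregate data, and 5.9 does the same for individually randomised women who return no sample, whereas 9.2 allows pseudonymised line-level data. That conflict needs resolving, but aggregate counts by randomised group are enough for unadjusted risk differences.

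**Conclusion.** The point holds as one about a badly fixed analysis, of moderate weight. The synopsis ties a 2-df omnibus test to an undefined outcome, and 8.2 supplies no unconditional three-group outcome to match it.

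On self-sample return, the test is uninformative: power is about 100% even with B = C. This rests on the 2:1:1 split of 5000 and on Group A returning no more than a few per cent. On any screening, the test can succeed or fail (19% to above 99.9% in the scenarios tried, all with assumed cytology uptake), but it estimates neither the letter-versus-kit difference nor the gain over usual care.

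The design can address the first question well if the protocol's own 12% and 7% are about right, and less well if the true gap is 2 or 3 points. The calculations do not establish precision for the comparisons with usual care, because that depends on a cytology uptake which the protocol does not state.

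**What to change.** 1. Define screening uptake in the synopsis and 8.2 as cytology or self-sample within a fixed window from randomisation, and state the window.
2. In both places, replace the 2-df test with risk differences and 95% confidence intervals by randomised group:
   - C minus B, self-sample returned within 6 months of invitation (the Appendix 1 window);
   - B minus A and C minus A, any screening within the window fixed in step 1.
3. In 8.2, make screening status by randomised group a planned outcome rather than one that depends on whether extraction proves possible.

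Adjustment for multiplicity and stratification by practice may be added but are not needed in a pilot without a formal primary outcome.

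The cost is a change of wording, a little extra analysis, and cytology counts for Group A within the window. Section 9.2 already plans to collect cytology data for all women in the study. The practices' searches would have to return counts by randomised group and time since randomisation.

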#### 5.3. Individual-level randomisation

Eligible women will be identified on a monthly basis using GP records (i.e. date of last cytology test entered will be used to calculate time since last test). This will be carried out by a member of the GP practice admin team using a pre-written search of the electronic GP records. All eligible women in participating GP practices who have never been screened or who reach the 15 month (or 27 month) anniversary of their last test due date and have not been screened (by cytology or self-sample) will be randomised (2:1:1) to receive usual care (Group A), a letter inviting them to order a self-sampling kit (Group B) or a self-sampling kit

(Group C). This will include women who have been offered self-sampling opportunistically in the intervention arm GP practices.

GP practices will randomise eligible women either using a computer-generated list of random numbers that will be provided by the study team or using the in-built randomise function in the EPR. We will use a mailing company (PSL Print Management Ltd) to assemble kits and subsequently distribute letters and kits to women on the GP practices' behalf. This vendor is fully ISO27001 and GDPR compliant. It will be recommended to GPs that they should put a data notice on their website / in the practice stating that patient's data may be submitted to a third-party organisation as part of a cervical screening research study.

A patient information leaflet, a self-sample instruction sheet and an HPV information leaflet will be included with the invitation letters sent to women in Groups B and C.

Women invited to order kits (Group B) will be able to choose from different options for ordering kits. The currently planned options include:

- Ordering kits online (from a secure website)
- Ordering kits by returning a mail order form (using a freepost envelope)
- Ordering kits by text message

The inclusion of ordering kits by text message will depend on each GP practices preferences and existing text message software. There are several different platforms available for text messaging at GP practices, capability/functionality varies, and some practices may not use text messages at all. We envisage that the process will comprise a weekly email of text message replies (auto-generated by the text message platform) that is sent to a member of the GP practice admin team who will then send out kits.

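### Groups A, B and C are randomised within each practice but compared by a pooled chi-square that does not use practice; the test is valid, and stratifying it by practice would be a small, free improvement

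*Protocol*

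**What the plan says.** Protocol section 4 describes the allocation: "The second (nested) randomisation will be individual level randomisation of women within each GP practice". It gives one ratio for all practices and all routes of entry: "Individual-level randomisation of women will be in the ratio of 2:1:1 to either" usual care, a letter inviting the woman to order a kit, or a posted kit. Section 5.3 has the practices carry it out: "GP practices will randomise eligible women either using a computer-generated list of random numbers" supplied by the study team, or using the randomise function of their record system. It is done in rounds: "Eligible women will be identified on a monthly basis using GP records". No blocking is described, and no stratification other than the within-practice conduct.

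For the comparison, the synopsis (Statistical Methodology and Analysis) states: "Screening uptake between the three arms of the individual level randomisation will be compared by a Chi-square test" on 2 degrees of freedom. Section 8.2 repeats the choice: "The Chi Squared test will be used to determine the" differences in proportions between groups. Neither sentence has a practice term. Section 8.2 does say that the uptake measures will also be examined by practice, age and screening status, and that this pilot has no formal primary outcome measure.

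**The concern.** When allocation is carried out separately in each practice, the comparison that uses the design most fully is made within practices and then combined. One 3×2 table leaves differences between practices in the error term.

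The protocol gives reasons to expect such differences:

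- Practices are themselves randomised to offer kits opportunistically or not, and women already offered a kit that way still enter the individual randomisation (section 5.3).
- Text ordering depends on each practice's preferences and software (section 5.3).
- Text reminders go out only where the practice already uses messaging software (section 5.6).

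At stake is a little power and, if allocation is balanced within practice, an actual significance level slightly below the nominal one. This concerns the individual randomisation only. It is separate from clustering in the practice-level comparison.

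**Working it through.** **The plan's own figures.** Three groups by a yes/no outcome give (3 − 1) × (2 − 1) = 2 df, so the stated 2 df is that of the plain pooled table. A stratified general-association test also has 2 df, so the df alone would not exclude stratification; it is the wording that names no strata. No power, effect size or ICC is stated for this test.

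**Inputs from section 8.1.2.** About 5000 women in 13 practices, about 385 each. At 2:1:1 this is 2500 in A and 1250 each in B and C, which agrees with the 1250 letters and 1250 kits in that section. (The same section also puts 2500 in each intervention arm, which 5000 at 2:1:1 cannot give. That is a separate matter.) Assumed uptake is 7% in B and 12% in C.

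**Assumptions not in the documents.** ICC of 0 to 0.05 between practices; 8% uptake in every group under the null; 7%, 8% and 10% in A, B and C under the alternative; two equal entry cohorts with a log-odds gap of 0.7.

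**Tests compared.** The pooled Pearson chi-square was set against the 2-df Cochran-Mantel-Haenszel (CMH) statistic Q = d′V⁻¹d. Here d sums, over strata k, the observed minus expected returns, Y_k − N_k·m_k/n_k, for two of the groups. V sums [m_k(n_k − m_k)/(n_k − 1)]·[diag(f_k) − f_k f_k′], with f_k = N_k/n_k. The strata were practice × the two assumed cohorts.

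**Type I error (3000 runs, simulation SE about 0.4 points):**

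| ICC | Simple randomisation: pooled / CMH | Balanced within stratum: pooled / CMH |
|---|---|---|
| 0 | 4.9% / 5.0% | 4.8% / 5.0% |
| 0.01 | 5.3% / 5.3% | 4.3% / 4.6% |
| 0.02 | 4.7% / 4.6% | 4.0% / 4.6% |
| 0.05 | 5.7% / 5.4% | 3.7% / 4.9% |

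**Check by formula, practice only.** If allocation is exactly balanced within practice, the pooled statistic behaves approximately as (1 − ICC) times a chi-square on 2 df. Its rejection rate is then 0.05^(1/(1 − ICC)): 4.9% at ICC 0.01, 4.7% at 0.02 and 4.3% at 0.05. The simulated values are somewhat lower. The simulation also balanced on cohort, and there is simulation error. The direction is the same and the size is small either way.

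**Power of the three-group test (2000 runs):**

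| ICC | Simple: pooled → CMH | Balanced: pooled → CMH |
|---|---|---|
| 0 | 83.0% → 83.5% | 81.7% → 81.9% |
| 0.01 | 83.8% → 84.7% | 83.8% → 84.5% |
| 0.02 | 82.3% → 83.7% | 82.3% → 83.4% |
| 0.05 | 84.2% → 86.5% | 83.8% → 86.4% |

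The gain is about 0–1.5 points up to ICC 0.02 and about 2.5 points at 0.05. Because the strata included the assumed cohorts, practice alone gives somewhat less at the low end. Treating practice strata as multiplying the sample size by 1/(1 − ICC), a comparison of 2500 with 1250 women at an assumed 5% versus 7% moves from 69.5% to 69.9%, 70.3% and 71.6% at ICC 0.01, 0.02 and 0.05. Those are gains of 0.4, 0.8 and 2.1 points.

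**On the protocol's own rates.** B versus C at 7% and 12% with 1250 each has power of about 99% without adjustment.

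**The case against.** The strongest reply is that the pooled chi-square is a valid analysis of an individually randomised comparison, and that the rest is preference. That stands as to validity. A reader might infer that the analysis does not follow the randomisation, or that it is valid only if the realised ratio is equal in every practice. The documents do not support either. What matters is the allocation probability, which is 2:1:1 for every practice and route of entry, and chance variation in realised counts is already covered by the test's error rate. A reader might also infer bias from the two local methods of randomising. That would need a method that fails to deliver 2:1:1, and nothing in section 5.3 suggests one.

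Other parts of the reply:

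- **Between-practice variation is unknown.** Correct: no ICC is given. The background section says that return among women offered a kit was constant across practices in the earlier study. It also says that offering ranged from 11% to 36% between practices, so variation in overall uptake is plausible but not quantified.
- **Section 8.2 already looks at practice.** It does, but descriptively. That does not stratify the named comparison.
- **This belongs in the statistical analysis plan.** In part. But the protocol does not leave the test open. It names one, without strata, in two places, so a stratified analysis plan would have to depart from that wording.
- **Data may be limited.** Sections 5.9 and 10.5 speak of aggregate data only for women who return no sample or are in usual care, while section 9.2 also allows pseudonymised line-level data. Counts by practice and group are aggregate, so the stratified test is feasible under either reading.

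**Conclusion.** The point holds as a minor recommendation, not as an error. The stated test is valid. It leaves unused the practices within which women were randomised, at a cost of about 0–1.5 points of power at ICC up to 0.02 and about 2.5 points at 0.05. It is slightly conservative only if allocation is balanced within practice (simulated 3.7–4.3% at ICC 0.01–0.05), and the protocol does not state such balance. All these sizes rest on assumed ICCs and uptake rates and, in the simulation, on an assumed cohort effect.

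Entry cohort (never screened, 15-month, 27-month) might be taken for a second randomisation stratum. Section 4 describes it as a route and time of eligibility, with no stratified allocation, so it is an optional prognostic covariate that the design does not require. In a pilot without a formal primary outcome, no main conclusion is likely to change.

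**What to change.** In the synopsis and in section 8.2, replace the pooled chi-square for the individually randomised women with a test stratified by practice, for example Cochran-Mantel-Haenszel on 2 df. Report practice-stratified risk differences between groups with 95% intervals, which also serve the pilot's estimation aim better than a 2-df p-value. Entry cohort may be added as a covariate if the counts are extracted that way.

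The cost is one sentence in each place. The analysis needs only the number randomised and the number screened in each group at each practice, with no extra work for participants.
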